9.B. Participants: A total of 10 youth will be recruited to pilot test the procedures outside of the scanner (up to 5 HC and up to 5 with FAPD). Then, for the active part of the study, a total of 50 participants will be recruited (25 with FAPD and 25 HC). Children with FAPD will be recruited based on the presence of an FAPD diagnosis (see inclusion/exclusion criteria below). Healthy controls (HC) will not have an FAPD diagnosis.

Inclusion Criteria:

- a. Children (boys and girls) between 11-16 years of age and their parent/primary caregiver.
- b. Meets criteria for one of two study groups:
 - FAPD: based on physician diagnosis of FAPD confirmed by a validated Rome IV measure.
 - HC: based on a rule out of an FAPD diagnosis (using the Rome IV measure).

We will recruit approximately 50% of HCs with and without clinical levels of anxiety (e.g., SCARED cut-off score greater than or equal to 25) to match the anxiety levels anticipated in the FAPD group.

- c. Sufficient English language ability necessary to complete study measures and protocol

Exclusion Criteria

- a. Children with significant medical condition(s) with an identifiable organic cause including those that may account for abdominal pain symptoms (e.g., Inflammatory Bowel Diseases such as Ulcerative Colitis and Crohn's Disease). Rationale: Children with a significant medical condition may impact the study results. Further, youth with organic conditions that include abdominal pain may not meet criteria for FAPD even if they present with similar symptoms.
- b. Children with a documented developmental delay, autism spectrum disorder, a previously diagnosed thought disorder (i.e., psychosis), or bipolar disorder will be excluded. Rationale: These comorbidities may confound the study aims by impacting the dependent measures.
- c. Significant visual, hearing, or speech impairment. Rationale: Children will be excluded if they are not able to see the testing stimuli, hear the test examiner, or respond verbally to the test examiner, even with the help of corrective or assistive devices (e.g., glasses, hearing aids).
- d. Organic brain injury. Rationale: Children must not have a history of epilepsy, a head trauma associated with a loss of consciousness, or any other organic disorder since these conditions could possibly affect brain function and cognition and interfere with study results.
- e. *Other exclusionary criteria specific to the fMRI component of the study:

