Imaging protocol. Brain images will be acquired via a 2015 model Philips 3T Ingenia MRI system using a 32-channel head coil. Pain intensity/unpleasantness and state anxiety ratings will be acquired after each sequence. Imaging will occur using block design, and will include sequences obtained at rest, and in the presence/absence of the cognitive task (with and without water loading). The pilot testing phase will allow for refinement of a neuroimaging protocol for the active study.

9.C.3. Payment: Families will receive payment for this study in the form of a reloadable debit card (ClinCard). A handout will be given to families that will explain how to use the card. Because families are being paid for their participation, CCHMC is required by the Internal Revenue Service (IRS) to collect and use the participant’s social security number (SSN) or taxpayer identification number (TIN) to track the amount of money that they are paid. Families will need to complete a Federal W-9 form for this income tax reporting. This form requires the participant’s Social Security number. This form will be given to the CCHMC business office. It will not be kept as part of the participant’s study chart. Subjects will receive a \$25 incentive for their screening visit. Participants recruited to participate in the pilot testing phase (no MRI) will be compensated \$50. We will reimburse families and participants who are recruited as part of the active research project for the visit that includes the MRI an additional \$100.

9.D. Measures: *Standardized, psychometrically validated* instruments used in prior pediatric pain studies will be used. These measures will be administered using the REDCap data capture platform.

Screening:

FAPD questionnaire (57). Measure to confirm diagnosis of FAPD based on Rome IV diagnostic criteria.

Screen for Child Anxiety Related Disorders (SCARED) (58, 59). A 41-item measure of anxiety over the past 3 months for children ages ≥ 8 (60). Scores ≥ 25 = clinical anxiety cut-off. The SCARED was validated in pediatric pain (61), and >50% of children with FAPD experience clinical anxiety, which is related to higher pain/disability (9). If this measure is not obtained clinically, it will be administered as part of the research protocol.

MRI Safety and Screening. Research staff to determine if patient can safely complete fMRI protocol.

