9.E. Data Analysis: For the fMRI data, image processing and data analysis will be accomplished using FSL (70). Each subject’s functional images will be registered to their structural data using a six-parameter linear 3-D transformation and then nonlinearly warped to standard space (MNI152) (71-73). The aCompCor approach will be used to preprocess BOLD data for functional connectivity and psychophysiological interaction analyses (74). This process minimizes the impact of global signal changes as well as signal changes induced by movement and other sources of noise. Analyses of data will be accomplished via mixed effects ANOVAs. Pain-related activation will be identified in images by comparing pre vs. post water loading data within subjects. These findings will then be contrasted across FAPD and HC groups. Multiple regression analyses will be used to examine if the changes in brain regions are related to the pain intensity/unpleasantness/anxiety. Next, changes in pain-related brain activation and functional connectivity *during* the cognitive task following the WL-SPT will be examined. There will also be a wealth of data available for exploratory analysis. Such analyses may include examining resting state FAPD data vs. HC data and exploring groups by anxiety level.

9.F. Sample Size: Analyses were powered to address pain intensity/unpleasantness differences measured during the pilot WL-SPT study (67). A Monte Carlo simulation was performed to obtain a power estimate for the analyses under the following assumptions: 1) equivalent sample sizes for the two groups, 2) covariates (age, gender, ethnicity, SES, baseline pain) will explain ($R^2 = 0.35$) 35% of the variance, and 3) an effect size difference between FAPD and HC of $d = 0.73$ is observed. Monte Carlo simulation results showed power >0.80 to detect a $d = 0.55$ difference if 20 per group (total $N = 40$) are available for analysis after proper handling of missing data. Additional power calculations using

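### The power above 0.80 claimed in 9.F for d = 0.55 with 20 per group does not follow from its stated inputs (about 0.50 to 0.55), and 9.E writes no pain-rating group model for it

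*Combined protocol and SAP*

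**What the plan says.** Section 9.F opens its justification with "Analyses were powered to address pain intensity/unpleasantness differences" seen in the pilot water-load study. It lists three assumptions:

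- equal group sizes;
- "covariates (age, gender, ethnicity, SES, baseline pain) will explain ($R^2 = 0.35$) 35% of the variance";
- "an effect size difference between FAPD and HC of $d = 0.73$ is observed".

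It then reports the result for a different effect size: "Monte Carlo simulation results showed power >0.80 to detect a $d = 0.55$ difference if 20 per group". No alpha, sidedness, number of ratings or correlation between ratings is given for this simulation. The 0.05 level in 9.F belongs to the separate imaging calculation that follows.

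Section 9.B recruits 25 per group. With the 20% data loss allowed for in 9.F, 50 × 0.80 = 40 remain, or 20 per group.

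Section 9.E begins "For the fMRI data, image processing and data analysis will be accomplished using FSL". It has one general sentence naming mixed-effects ANOVA, then contrasts before/after water-load activation between groups. Pain ratings appear by name only here: "Multiple regression analyses will be used to examine if the changes in brain regions are related to the pain intensity/unpleasantness/anxiety". Under the imaging protocol in 9.C.2, "Pain intensity/unpleasantness and state anxiety ratings will be acquired after each sequence".

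**The concern.** Two things do not fit together. First, the effect size assumed (0.73) is not the one for which power is reported (0.55), and the reported power looks far too high for the smaller value with 40 participants. Second, the power statement concerns a covariate-adjusted group comparison of pain ratings, and the analysis section does not write that comparison down.

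This calculation is the first of two justifications for 40 analysable participants. If the claim is wrong, a reader who sees no group difference in ratings may conclude that the water load provoked similar pain in both groups, believing that a difference of 0.55 SD had less than a 20% chance of being missed.

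**Working it through.** **Inputs from the document.** n = 20 per group analysed; d = 0.55 (and 0.73); R² = 0.35; five covariates (9.F). Recruited n = 25 per group (9.B).

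**Inputs assumed.** Alpha 0.05, two-sided unless stated; one rating per child; d on the SD of a single rating; covariates unrelated to group apart from chance imbalance.

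**Formula.** Noncentrality = d / √(1 − R²) × √(n/2), with 2n − 7 degrees of freedom (two group means and five covariates).

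**Attempt to reproduce the plan's figure (d = 0.55, n = 20).** 0.55 / √0.65 = 0.682; 0.682 × √10 = 2.157. With 33 df the two-sided critical value is 2.035, and power is **0.553**. A simulated ANCOVA (40,000 runs, five random normal covariates) gives **0.497**; it is lower because chance covariate imbalance costs precision that the formula ignores. The stated figure is above 0.80.

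**Variations on the same inputs** (simulated to noncentral t):

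| d | n per group | Two-sided 0.05 | One-sided 0.05 |
|---|---|---|---|
| 0.55 | 20 | 0.50 to 0.55 | 0.63 to 0.68 |
| 0.55 | 25 | 0.61 to 0.66 | 0.73 to 0.77 |
| 0.73 | 20 | 0.74 to 0.79 | 0.83 to 0.88 |
| 0.73 | 25 | 0.84 to 0.88 | 0.91 to 0.93 |

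Without covariates, d = 0.55 at 20 per group gives 0.40 two-sided. No row at d = 0.55 reaches 0.80. For d = 0.73 at 20 per group the noncentrality is 0.73 / √0.65 × √10 = 2.863, giving 0.794.

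**Detectable d at 0.80 power, two-sided, R² = 0.35.** At 20 per group: 0.74 (noncentral t) to about 0.79 (simulated). At 25 per group: 0.65 to about 0.69. By noncentral t, d = 0.55 would need about 35 analysed per group.

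**What would give 0.80 at d = 0.55 with 20 per group, two-sided.** Each route uses a value the document does not give.

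- *Higher R²:* about 0.64 (noncentral t) to 0.68 (simulated), against the stated 0.35.
- *Change score without covariates,* effect d / √(2(1 − ρ)): 0.40 at ρ = 0.5, 0.59 at ρ = 0.7, and 0.80 only at ρ of about 0.82. If R² = 0.35 is also applied to the change score, ρ = 0.7 gives 0.77 and ρ = 0.8 gives 0.91 (noncentral t). That may count baseline pain twice.
- *Mean of m ratings,* SD √((1 + (m − 1)ICC)/m), with R² = 0.35: at ICC 0.3, three ratings give 0.76 to 0.82 and four give 0.80 to 0.86. At ICC 0.5 to 0.7, three or four ratings give 0.59 to 0.75.

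**The model in 9.E.** The group contrasts spelled out there are of brain activation. The ratings enter as variables related to brain change. The general mixed-effects ANOVA sentence names no rating outcome, no group term for ratings and no covariates. The covariate set used in the power calculation is listed only in 9.F.

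**The case against.** The strongest reply is that 0.50 to 0.55 rests on choices 9.F does not make: two-sided 0.05 and a single rating. Ratings are taken repeatedly, so a repeated-measures simulation would suit the design, and the mixed-effects ANOVA sentence could be read to include the ratings. The stated aims are directional, and combining one-sided testing with averaged ratings passes 0.80 more easily: by noncentral t, three ratings give 0.89 at ICC 0.3 and 0.83 at ICC 0.5. The separate imaging calculation, which asks for 35 subjects, also supports 40 and lies closer to the hypotheses.

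Much of this stands as a limit on the claim. It is not shown that the simulation was run wrongly, and unstated inputs could have produced the figure. But it does not rescue the text. Every route to 0.80 needs a correlation, R² or number of ratings that the document omits; one-sided testing alone stays at 0.63 to 0.68; and the change from 0.73 to 0.55 remains unexplained. Reading the ANOVA sentence generously still supplies no outcome or covariates.

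The detectable effects above also assume covariates unrelated to group. The groups are defined by a pain diagnosis, so baseline pain may differ between them. Adjusting for it would then lower power further.

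**Conclusion.** The concern holds. On the inputs 9.F states, with two-sided 0.05 and a single rating assumed, power at d = 0.55 with 20 per group is about 0.50 to 0.55. A true difference of that size would be missed in about 45% to 50% of studies, not in fewer than 20%. The shortfall of 25 to 30 percentage points is too large for sidedness alone to explain. The claimed power fits d = 0.73 better, so 0.55 may be a slip or a value on another scale; the document does not say which.

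The consequence is moderate. No hypothesis from H1a to H2c is a group difference in ratings, the imaging calculation is separate and is not questioned here, and at d = 0.73 with 25 per group and the covariates, power is adequate (0.84 to 0.88). The correction should be made, but it does not put the design in doubt.

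**What to change.** In 9.F, rerun the simulation and state alpha, sidedness, the outcome (single post-load rating, change, or mean of several ratings) and any assumed correlation between ratings. Say how d = 0.73 and d = 0.55 relate. Then restate the power reached, or the detectable effect: for 0.80 power at 20 per group with R² = 0.35, about d = 0.74 to 0.79 under the assumptions above, noting that a baseline-pain difference between groups would raise it. If unstated inputs did give more than 0.80 at d = 0.55, stating them is enough.

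In 9.E, add one sentence giving the FAPD versus healthy-control model for the pain ratings to which this power refers, with the five covariates 9.F already names and baseline pain entered only once.

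The cost is one rerun, a few lines in 9.F and one sentence in 9.E, using variables already planned for collection. The drawbacks are a probably less favourable stated power and five residual degrees of freedom spent on covariates. No extra enrolment is asked for.

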<http://neuropowertools.org/neuropower/neuropowerinput> were conducted based on neuroimaging data available from [name] (mentor). *For between group changes*, data comparing youth with chronic pain (migraine) to healthy controls was utilized. Based on these data showing moderate to large effect size differences, a total of 35 subjects are required for power of .8 and $p < 0.05$. Thus, a total sample size of at least 40 (which assumes 20% of data will be lost due to motion and other artifacts) ensures adequate power to observe at least moderate effects. Furthermore, 10-15 per group is sufficient to detect differences in child (75, 76) and adult (77) fMRI studies.

10. Security: To minimize risk to confidentiality, every effort will be made to ensure that research data are kept confidential and stored so that data cannot be accessed by individuals who are not part of the research team. All project staff will be required to take the Collaborative Institutional Training Initiative (CITI) course on research responsible conduct. Research personnel will be informed of the study aims and procedures, with particular attention given to the importance of confidentiality. Unique identification numbers will be assigned to participants, and all data forms will be coded with this number rather than a name. A master list linking the identification number to participant names will be locked in a file cabinet in [name]

office separate from the study data. Access to the master list will be limited to key study personnel. Upon study completion, all study materials and participants' personal information will be destroyed. Locked filing space within [name] research laboratory will be identified and used exclusively for study purposes. CCHMC IRB approval will be obtained for this study prior to participant recruitment and data collection, and the IRB will be immediately informed of any adverse events that occur across the duration of the proposed study. In addition to the licensed clinical ([name]) and medical (Drs. [name] and [name]) providers, [name] herself is a licensed clinical psychologist and has a wealth of experience in conducting research involving vulnerable populations (e.g., children) and sensitive topics (e.g., anxiety).

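### Section 9.F says at least 40 participants secure power for moderate between-group imaging effects, but gives no effect size; 20 per group has 80% power only at d of about 0.9 (single two-sided 0.05 test)

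*Combined protocol and SAP*

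**What the plan says.** H1a and H1b in Section 2.A are FAPD versus HC hypotheses about activation and amygdala-prefrontal connectivity after the water load. Section 9.E describes the contrast in two steps: "Pain-related activation will be identified in images by comparing pre vs. post water loading data within subjects", and then "These findings will then be contrasted across FAPD and HC groups". The tested quantity is therefore a pre/post change compared between two groups.

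Section 9.F first powers the pain ratings. It assumes equal groups and that "covariates (age, gender, ethnicity, SES, baseline pain) will explain" 35% of the variance, and it names effect sizes of 0.55 and 0.73. It then adds a separate imaging calculation for between-group changes, made with an online imaging power tool, for which "data comparing youth with chronic pain (migraine) to healthy controls was utilized". The result is given as: "Based on these data showing moderate to large effect size differences", "a total of 35 subjects are required for power of .8" at p < 0.05. From this it concludes that a total of at least 40, allowing for 20% data loss, "ensures adequate power to observe at least moderate effects". A closing sentence cites earlier fMRI studies with 10 to 15 per group. Section 9.B plans 25 participants per group, 50 in all, for the active phase.

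**The concern.** The imaging calculation is the only one in Section 9.F that addresses H1a and H1b, and its conclusion is categorical. Yet the text reports no numeric effect size, sidedness, significance threshold or multiplicity setting for it. The source data are described as showing moderate to large effects, while the conclusion promises power for effects that are at least moderate, which is the lower end of that range. Five participants above the 35 cannot by themselves extend power to the lower end.

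What is at stake is how the results are read. The protocol does not say how a null FAPD versus HC contrast will be interpreted. A reader who trusts this sentence could take a null result as evidence against a moderate difference when the sample gives little such evidence.

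**Working it through.** **Inputs from the documents**
- Power 0.80, alpha 0.05 (9.F, imaging). Sidedness is not stated.
- Equal groups (9.F, pain-rating simulation). 50 recruited (9.B) and 20% loss (9.F): 50 × 0.8 = 40 analysable, or 20 per group.
- R² = 0.35 with five covariates (9.F, pain ratings only). Using it for imaging is a concession to the plan.

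**Assumptions**
- Moderate means d = 0.5 in the analysed measure; the documents do not define it, so a range is shown.
- One test, with no correction across regions or voxels.

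**Formula.** Two-sample noncentral t with n per group: ncp = [d/√(1 − R²)] × √(n/2), df = 2n − 2 − k, where k = 5 when R² is used and 0 otherwise.

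**The plan's own figure.** The 35 cannot be reproduced without its effect size. Read as a plain two-group comparison (18 and 17), 35 participants have 80% power at d = 0.98 two-sided or 0.86 one-sided. Moving to 40 lowers the two-sided value only to 0.91.

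**Power at d = 0.5, n = 20 per group**
- No covariates: ncp = 0.5 × √10 = 1.581, df = 38. Power is 0.338 two-sided and 0.463 one-sided.
- R² = 0.35: 0.5/√0.65 = 0.620; ncp = 0.620 × √10 = 1.961; df = 33. Power is 0.478 two-sided and 0.609 one-sided.

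**Across effect sizes, n = 20 per group**

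| d | Two-sided, no covariates (least favourable) | One-sided, R² = 0.35 (most favourable) |
|---|---|---|
| 0.4 | 0.23 | 0.46 |
| 0.5 | 0.34 | 0.61 |
| 0.6 | 0.46 | 0.75 |
| 0.8 | 0.69 | 0.92 |

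**Detectable difference and sample size**

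| | Two-sided | One-sided | Two-sided, R² = 0.35 | One-sided, R² = 0.35 |
|---|---|---|---|---|
| d with 80% power, 20 per group | 0.91 | 0.80 | 0.74 | 0.65 |
| n per group for d = 0.5 at 80% | 64 | 51 | 42 | 33 |
| Power at d = 0.5, all 25 per group | 0.41 | 0.54 | 0.57 | 0.70 |

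**If d = 0.5 is on the raw scale.** Power then depends on the pre/post correlation ρ, which the plan does not state.
- Change score: the effect becomes 0.5/√(2(1 − ρ)). Two-sided power is 0.34 at ρ = 0.5, 0.51 at 0.7 and 0.68 at 0.8. It reaches 0.80 at ρ of about 0.85 (0.81 one-sided).
- Baseline-adjusted: the effect becomes 0.5/√(1 − ρ²), df = 37. Power reaches 0.80 at ρ of about 0.84 two-sided or 0.78 one-sided.

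**If 40 is the count before loss.** 40 × 0.8 = 32 remain, fewer than the 35 the plan says it needs. With 16 per group the two-sided detectable d is about 1.02.

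**The case against.** The strongest reply is that d = 0.5 is not in the documents. The only effect sizes in Section 9.F are 0.55 and 0.73, both for pain ratings. At d = 0.73 with R² = 0.35, 20 per group has power of 0.79 two-sided and 0.88 one-sided. If moderate meant something near 0.7, and the imaging contrasts were covariate-adjusted, the sentence would be close to right. This stands as a limit on the power figures. It does not rescue the sentence, because the plan neither defines moderate that way nor specifies those covariates, or a one-sided test, for imaging. Without them, moderate would have to mean about 0.9.

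Three stronger readings are tempting, and the documents support none of them.
- A reader might infer that the imaging tool's answer of 35 is wrong. Its inputs and output are not in the documents, it need not compute a plain t-test, and 35 may be right for the effects in the migraine data.
- A reader might notice that a one-sample or paired test with 35 participants has 80% power at d of about 0.49, and infer that the wrong design was used. The text applies the 35 to between-group changes and gives nothing to confirm such a slip.
- A reader might take 0.61 as a ceiling. It holds only for 40 analysed, R² = 0.35 and d = 0.5 in the analysed measure. With all 50 analysed it is 0.70, and on the raw scale a high pre/post correlation would raise it further.

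It is also fair to say that Section 9.F presents the imaging calculation as additional to the pain-rating one, and that it cites studies with 10 to 15 per group. Those citations are precedent and not a power calculation.

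**Conclusion.** The statement is unsupported as written, and it fails on the conventional reading of moderate. With 20 analysable per group and a single uncorrected two-sided 0.05 test, 80% power is available at d of about 0.91, and at 0.65 even with both concessions. If the true difference in the analysed measure is 0.5, it would be missed in 39% (1 − 0.61) to 66% (1 − 0.34) of such studies, against the 20% implied by the 0.80 target. Correction across regions or voxels would lower power further.

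This rests on 40 being the analysable count and on d being measured on the analysed change. It applies to H1a and H1b. Section 2.A does not make clear whether H2a and H2b are within FAPD or FAPD versus HC, so they are left open. A reader might infer that the study must be enlarged; that does not follow. What needs correcting is the stated sensitivity and the missing inputs.

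**What to change.** In Section 9.F:
1. Delete the reference to at least moderate effects and state instead: *With 20 analysable participants per group, a single uncorrected two-sided test at 0.05 has 80% power for a between-group standardised difference of about 0.9 in the analysed measure, and less after multiplicity correction.*
2. State that 40 is the count remaining after 20% loss from 50. If it is meant as the count before loss, reconcile the 32 that remain with the 35 required, and give the detectable difference as about 1.02.
3. Report the effect size, sidedness and threshold behind the 35.
4. Quote a smaller detectable effect only if a one-sided test or covariate adjustment is actually specified for the imaging contrasts in Section 9.E.

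The cost is a few sentences and a less favourable stated sensitivity. Sample size and procedures do not change.
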